## **6.11. Early Termination Procedures**

A subject who terminates from the study prior to Visit 8 should return to the site to complete the procedures for Visit 8/ET and Visit 9 follow-up. A subject who terminates from the study after Visit 8 should return to the site to complete the procedures for Visit 9 follow-up. All subjects who complete study treatment should be encouraged to return for Visit 10 (12 weeks post-treatment). Study personnel should make every effort to conduct all protocol-specified procedures to complete the study. Every effort should also be made to obtain a final MRI.

## **7. TREATMENT OF SUBJECTS**

### **7.1. Description of Study Drug**

Refer to [Section 8.1](#) for information on the study drug.

### **7.2. Concomitant Medications**

A review of concomitant medications will be conducted during the screening period.

The Investigator should instruct the subject to notify the study site about any new medications he/she takes after the start of the study or any medications they have stopped using.

All medications and significant non-drug therapies (including physical therapy and blood transfusions) administered from the time the ICF is signed through Visit 10 or ET must be listed on the Concomitant Medications/Therapy eCRF.

### **7.3. Prohibited and Permitted Treatment**

The following treatments are prohibited:

- Prior investigational drug use within 4 weeks or 5 half-lives (whichever is longer) before Baseline
- Use of pexidartinib, any other oral tyrosine kinase inhibitor (e.g., imatinib or nilotinib), or any biologic treatment targeting CSF1 or CSF1R within 3 months before Baseline and for the duration of the study

### **7.4. Treatment Compliance**

Subject compliance with study treatment will be monitored by site staff administering study drug injections.

## **8. STUDY DRUG MATERIALS AND MANAGEMENT**

### **8.1. Study Drug, Labeling, Packaging, and Dispensing**

AMB-05X drug substance is a human monoclonal antibody against CSF1R.

Study drug is packaged as a [REDACTED] of [REDACTED] mL of [REDACTED] mg/mL in [REDACTED] mL glass vials. AMB-05X vials will be stored [REDACTED] °C until use.

### **8.2. Study Drug Storage**

Study drugs must be received at the study site by a person designated by the study team, handled and stored safely and properly, and kept in a secured location that only the Investigator and designated staff can access.

Upon receipt, AMB-05X should be stored between [REDACTED] °C protected from light and according to the storage and expiration (where required) information provided on the label in the original container.

Storage conditions must be adequately monitored, and appropriate temperature logs maintained as source data.

### **8.3. Study Drug Administration**

After confirmation of enrollment eligibility at Visit 2 (Baseline), subjects will be enrolled into the study and receive the first dose of study drug.

The study will begin dosing AMB-05X at 150 mg administered via intra-articular injection to the affected joint. Based on ongoing review of the available safety, PK, PD, and efficacy data, the Sponsor may decrease the dose to 90 mg or increase the dose to 210 mg in subsequent subjects. A separate Study Drug Administration Instructions will be provided with detailed study drug administration procedures.

A single vial will be removed from the kit [REDACTED]

[REDACTED] prior to administration. [REDACTED] [REDACTED], diluted with [REDACTED] mL normal saline (0.9% NaCl solution), and mixed gently prior to injection. AMB-05X must be administered within [REDACTED] hours from the beginning of the warming procedure. For a dose of 150 mg, a total of [REDACTED] mL of the diluted solution will be withdrawn from the vial in a sterile syringe and administered via an intra-articular injection to the affected knee joint. For a dose of 210 mg, [REDACTED] mL of the diluted solution will be withdrawn, and for a dose of 90 mg, [REDACTED] mL of the diluted solution will be withdrawn.

Eligible subjects will receive the intra-articular injection of AMB-05X to the affected knee joint once every 2 weeks for 12 weeks (for 6 treatments total). The Sponsor may change the dose based on its own ongoing review or periodic DMC review of available data (each time 3 new subjects complete study treatment).

Study drug will be administered at the study center by qualified study staff. Subjects will remain at the study center for a minimum of 90 minutes after dosing to monitor for any adverse reactions, including any injection-site reactions.

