Study Design	
This is a multicenter study with an adaptive design that will enroll approximately 12 subjects with TGCT of the knee for 12 weeks of multiple-dose, open-label treatment with AMB-05X.
 
The study schema is provided in Section 1.2, and the Schedule of Events is provided in Section 1.3. There will be a screening period of up to 4 weeks, a treatment period of 12 weeks, and a post-treatment follow-up period of 12 weeks. Clinic visits will occur at Screening (Visit 1, within 4 weeks prior to Baseline); Baseline/Week 0 (Visit 2, when subjects receive their first injection of AMB-05X); Week 2 (Visit 3); Week 4 (Visit 4); Week 6 (Visit 5); Week 8 (Visit 6); Week 10 (Visit 7, when subjects receive their last injection of AMB-05X); Week 12 (Visit 8, end of treatment period and assessment of primary and secondary endpoints); Week 14 (Visit 9, for post-treatment follow-up 2 weeks after completing the treatment period); and Week 24 (Visit 10, for final post-treatment follow-up 12 weeks after completing the treatment period).
 
The study will begin dosing AMB-05X at 150 mg administered via intra-articular injection to the affected knee joint. Subjects will receive an injection of AMB-05X once every 2 weeks for 12 weeks (for 6 treatments total).
 
Safety, pharmacokinetics (PK), pharmacodynamics (PD), and efficacy assessments will be reviewed by the Sponsor on a continuous, subject-by-subject basis to determine whether the assigned dose is appropriate. Depending on these results, the Sponsor may either decrease the dosage strength to 90 mg or increase the dosage strength to 210 mg in subsequent subjects who enroll. In general, subjects are expected to complete the study at the dose strength which they started the study, unless they experience a clinically significant AE that would warrant a dose reduction. As a general rule, clinically significant AEs include, but are not limited to, any AE considered to be at least possibly related to study drug and severe in intensity or meets the criteria for a SAE. Subjects who are unable to tolerate a dosage strength of 90 mg will be withdrawn from the study.
 
When at least 3 subjects have completed Week 6, a data monitoring committee (DMC) will review the available safety, tolerability, PK, PD, and efficacy data. Study enrollment and conduct may continue unchanged during DMC review. Based on the recommendations of the DMC, the Sponsor may then implement any one of the following adaptive changes without a protocol amendment:
 

• Continuation of enrollment under the existing design, without any changes to the study.

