
	

Continuation of enrollment with a new dose. Specifically, the DMC may recommend a dose reduction to 90 mg or a dose increase to 210 mg in subsequent subjects. Subjects may not exceed a dose of 210 mg or go below a dose of 90 mg. Subjects who are unable to tolerate a dose of 90 mg will be discontinued from the study.

Discontinuation of further enrollment and/or suspension/termination of the study.

 
Thereafter, the DMC should continue to review available data on a regular basis throughout the study (each time 3 subjects complete study treatment) and provide ongoing recommendations regarding appropriate next steps in study conduct (as outlined above). If a change in dose is made during the study, the DMC will again review the available data when 3 subjects have completed Week 6 at the new dose and provide further recommendations as outlined above.

Dosage and Administration	
The study will begin dosing AMB-05X at 150 mg administered via intra-articular injection to the affected knee joint as described in Section 8. Subjects will receive an injection of AMB-05X once every 2 weeks for 12 weeks (for 6 treatments total). A total of 3 dose levels are permitted in this study: 90 mg, 150 mg, and 210 mg. Based on ongoing review of the available safety, PK, PD, and efficacy data, the Sponsor may decrease the dose to 90 mg or increase the dose to 210 mg in subsequent subjects.
 
Study drug will be administered at the study center by qualified study staff. Subjects will remain at the study center for a minimum of 90 minutes after dosing to monitor for any adverse reactions, including any injection-site reactions.

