Serum anti-AMB-05X antibody levels will be measured pre-dose at Week 0 and Week 10. Synovial anti-AMB-05X antibody levels will be measured pre-dose at Weeks 0, 4, and 10.

Safety, PK, PD, and efficacy assessments will be reviewed by the Sponsor on a continuous, subject-by-subject basis to determine whether the assigned dose is appropriate. Depending on these results, the Sponsor may either decrease the dosage strength to 90 mg or increase the dosage strength to 210 mg in subsequent subjects who enroll. In general, subjects are expected to complete the study at the dose strength which they started the study, unless they experience a clinically significant AE that would warrant a dose reduction. As a general rule, clinically

significant AEs include, but are not limited to, any AE considered to be at least possibly related to study drug and severe in intensity or meets the criteria for a SAE. Subjects who are unable to tolerate a dosage strength of 90 mg will be withdrawn from the study

When at least 3 subjects have completed Week 6, a data monitoring committee (DMC) will review the available safety, tolerability, PK, PD, and efficacy data. Study enrollment and conduct may continue unchanged during DMC review. Based on the recommendations of the DMC, the Sponsor may then implement any one of the following adaptive changes without a protocol amendment:

- Continuation of enrollment under the existing design, without any changes to the study.
- Continuation of enrollment with a new dose or dose frequency criteria. Specifically, the DMC may recommend a dose reduction to 90 mg or a dose increase to 210 mg in subsequent subjects. Subjects may not exceed a dose of 210 mg or go below a dose of 90 mg. Subjects who are unable to tolerate a dose of 90 mg will be discontinued from the study.
- Discontinuation of further enrollment and/or suspension/termination of the study

Thereafter, the DMC should continue to review available data on a regular basis throughout the study (each time 3 subjects complete study treatment) and provide ongoing recommendations regarding appropriate next steps in study conduct (as outlined above). If a change in dose is made during the study, the DMC will again review the available data when 3 subjects have completed Week 6 at the new dose and provide further recommendations as outlined above.

[figure not shown]
Refer to [Appendix 5](#) for potential changes to study conduct in the context of COVID-19 (coronavirus disease 2019).

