## 4.2. Rationale for Dose Regimen and Duration of Treatment

While AMB-05X has not been administered into the joints of TGCT patients, monoclonal antibodies (mAbs) have been used as intra-articular therapies at doses ranging from 10 to 600 mg, albeit more commonly at 100 to 150 mg in adults ([Wang, 2018](#); [Evans, 2014](#); [NCT01160822](#)). Moreover, another anti-CSF1R mAb has demonstrated preliminary efficacy administered systemically to TGCT patients ([Cassier, 2015](#)) thus supporting the class approach.

There is limited data in the literature on the synovial and systemic pharmacokinetics of antibodies following intra-articular administration, but based on the cynomolgus monkey results described above, published systemic PK with this mAb ([Papadopoulos, 2017](#)), and some published relevant modeling data ([Stepensky, 2012](#)), a projection of serum and synovial AMB-05X concentrations vs time following a first administration of 150 mg intra-articular is described in the figure below:

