#### 4.4. Treatment Assignment

This is an open-label study. Subjects will be initially assigned to receive 150 mg administered via intra-articular injection to the affected knee joint. Subjects will receive an injection of AMB-05X once every 2 weeks for 12 weeks (for 6 treatments total). The Sponsor may decrease the dose to 90 mg or increase the dose to 210 mg in subsequent subjects based on its ongoing review of the available data.

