### **6.5. Visit 5 (Week 6 ± 3 days)**

Complete the following procedures during the visit:

- Record any changes in concomitant medications since the previous visit.

- Record any AEs that may have occurred since the previous visit and follow up on the status of any existing AEs.
- Conduct a full physical exam and document any changes since the previous visit.
- Measure vital signs (blood pressure, heart rate, temperature, and respiratory rate) with the subject in a sitting position after having rested for 5 minutes.
- Obtain weight.
- Perform a 12-lead ECG.
- Collect a urine sample for urinalysis.
- Collect blood samples for clinical laboratory tests (chemistry and hematology).
- Collect synovial fluid for measurement of AMB-05X concentration and CSF1 levels prior to study drug injection.
- Perform MRI.
- Tumor assessment.
- Perform the following clinical assessments:
  - Worst stiffness NRS
  - PROMIS Physical Function Scale
  - BPI
  - EQ-5D-5L
  - Joint ROM
- Inject study drug.
- Observe subject for a minimum of 90 minutes after dosing to monitor for any adverse reactions, including any injection-site reactions.

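### The sponsor may raise later enrollees to 210 mg on its own review, before the first DMC review and before any scheduled post-dose laboratory test, ECG or MRI

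*Combined protocol and SAP*

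**What the plan says.** The sponsor's own route appears in four places. The synopsis and Section 4.1 describe continuous review, subject by subject, of safety, PK, PD and efficacy, after which "the Sponsor may either decrease the dosage strength to 90 mg or increase the dosage strength to 210 mg in subsequent subjects who enroll". Section 4.4 lets the sponsor "increase the dose to 210 mg in subsequent subjects based on its ongoing review of the available data". Section 8.3 puts the two routes in one sentence: "The Sponsor may change the dose based on its own ongoing review or periodic DMC review of available data".

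The DMC route is in the synopsis and Section 4.1: "When at least 3 subjects have completed Week 6, a data monitoring committee (DMC) will review" the accumulated data, and then "Based on the recommendations of the DMC, the Sponsor may then implement any one of the following adaptive changes", one of which is a new dose of 90 mg or 210 mg. Enrollment may continue during that review. After any dose change the DMC reviews again once 3 subjects have completed Week 6 at the new dose. No dose may exceed 210 mg.

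On prior experience, Section 4.2 begins: "While AMB-05X has not been administered into the joints of TGCT patients".

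**The concern.** The DMC rule looks like the checkpoint for a dose increase: three subjects followed to Week 6, when the first full set of post-dose assessments is due. The sponsor's route has no such checkpoint. Nothing in the protocol prevents a second or third subject from starting at 210 mg on a few weeks of data from the first.

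What is at stake is mainly local tolerability of repeated injections. The intra-articular monkey study (Section 2.3.4) reached about 160 mg human-equivalent, with one injection per knee in 4 animals, and 2 of the 4 had very low exposure at that dose. Other antibodies have been given into joints at 10 to 600 mg, more commonly 100 to 150 mg (Section 2.4.2), but they are different molecules. Neither source shows that 210 mg of this drug every 2 weeks is tolerated in a TGCT knee. Week 6 at 150 mg would be the first full check in these patients, and the increase need not wait for it.

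**Working it through.** The protocol gives no figure to reproduce here: about 12 subjects is stated without a formula, and no enrollment rate is given. The check compares the dose-change rules with the visit schedule, then works out timing under stated assumptions.

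**1. What each route requires before the first 210 mg dose**

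| Route | Where | Inputs named | Minimum subjects | Minimum follow-up |
|---|---|---|---|---|
| Sponsor | Synopsis, 4.1 | safety, PK, PD, efficacy | none | none |
| Sponsor | 8.3, synopsis dosing row | available safety, PK, PD, efficacy | none | none |
| Sponsor | 4.4 | available data | none | none |
| DMC | Synopsis, 4.1 | available safety, tolerability, PK, PD, efficacy | 3 | Week 6 |

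**2. What is scheduled after the first dose (Sections 1.3 and 6.2 to 6.5)**

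| Visit | Post-dose data first available |
|---|---|
| Week 0 | at least 90 minutes' observation; 2-hour serum PK and CSF1 |
| Week 2 (Day 15 ± 2) | AEs, vital signs, weight, serum and synovial PK and CSF1 |
| Week 4 (Day 29 ± 2) | AEs, vital signs, weight, synovial PK and CSF1, synovial anti-drug antibody |
| Week 6 (Day 43 ± 3) | first chemistry, hematology, urinalysis, ECG, physical examination, MRI, range of motion and patient-reported outcomes |

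The Visit 2 laboratory tests and ECG are taken before dosing. By the Week 6 assessments a subject has had injections at Weeks 0, 2 and 4: 3 × 150 = 450 mg, or 3 × 210 = 630 mg.

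**3. How early the increase could come**

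Assume even enrollment, one subject every d weeks. The DMC trigger falls at study week 2d + 6. Later subjects who could start at 210 mg before the first subject's Week 6 visit are those with k × d < 6, for k = 1, 2, and so on. This is an upper bound, because the sponsor needs some data from the first subject to review.

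| d (weeks) | DMC trigger (study week) | Enrolled before trigger, of 12 | Later subjects before first subject's Week 6 |
|---|---|---|---|
| 1 | 8 | 8 | 5 |
| 2 | 10 | 5 | 2 |
| 4 | 14 | 4 | 1 |
| 6 | 18 | 3 | 0 |

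**4. Size of the step**

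210 / 150 = 1.4. If the whole dose reached the circulation, 210 mg would be 210/60 = 3.5, 210/70 = 3.0 or 210/90 = 2.3 mg/kg (body weights assumed). The IV monotherapy study went to 20 mg/kg (Section 2.4.1.1).

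**5. Places left for 210 mg if the DMC must come first**

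Count 6 weeks from the third subject's first dose plus an assumed 2 weeks for the DMC, so 8 weeks, with 4.348 weeks per month. Places left = 12 − [3 + floor(8 / (4.348 / rate))], not below 0.

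| Subjects per month | 1 | 2 | 3 | 4 | 5 |
|---|---|---|---|---|---|
| Left, 2 weeks for the DMC | 8 | 6 | 4 | 2 | 0 |
| Left, 4 weeks for the DMC | 7 | 5 | 3 | 0 | 0 |

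**The case against.** The strongest reply is that this is a permissive adaptive design, stated consistently. A reader might infer from the two routes that the sections conflict, or that precedence between sponsor and DMC was left open by mistake. The documents do not support that. The sponsor decides under both routes, the DMC only recommends, and Section 8.3 offers the routes as alternatives.

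A reader might also infer that the sponsor could escalate blind. That goes too far. AEs, vital signs, injection-site observation, PK and CSF1 are all collected before Week 6. Unscheduled tests may be done to work up an event (Section 9.6.5). SAEs reach the sponsor within 24 hours (Section 9.6.6). The synopsis, 4.1 and 8.3 also name efficacy among the sponsor's inputs, and efficacy is first measured post-dose at Week 6, so a careful sponsor may well intend to wait. What survives is that waiting is not a condition: the review uses whatever data are available, and 4.4 does not mention efficacy.

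A third tempting inference is that missing early AST is a serious hazard, because treatment-related AST increase occurred in 7 of 25 (28%) IV monotherapy subjects. That rate pools IV doses up to 20 mg/kg. Section 2.3.5 reports very low serum exposure after intra-articular dosing in monkeys, no transaminase elevation at 1.5 mg/kg IV and limited AST elevation at 3 mg/kg IV. Section 2.3.3 describes reversible monkey enzyme rises with no microscopic liver correlate. Systemic risk therefore looks limited.

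Two further points stand. Week 6 data at 150 mg cannot establish tolerability at 210 mg. And three clean subjects exclude little: at an assumed 20% event rate the chance of seeing no event is 0.8³ = 51.2%. The benefit of the gate is that a full Week 6 assessment exists and the DMC has seen it, not that a given event rate has been ruled out.

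**Conclusion.** The concern holds as a modest safety gap. As written, the first increase to 210 mg can precede both the first DMC review and every scheduled post-dose laboratory test, ECG and MRI. The later DMC review at the new dose does not close the gap, because it comes only after 3 subjects have completed Week 6 at that dose.

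How many subjects this could affect depends on enrollment, which the protocol does not give: at most 5, 2 or 1 under the assumed spacings of 1, 2 or 4 weeks, and none at 6 weeks or more. The 210 mg cap, the 1.4-fold step, the restriction of increases to later enrollees and the low expected serum exposure all limit the consequence. This is a cheap improvement that the sponsor should make; it does not show that the design is unsafe or that its sections disagree.

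**What to change.** In the synopsis and Sections 4.1, 4.4 and 8.3, replace the sponsor's unconditional power to increase with wording such as:

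> On its own ongoing review the Sponsor may reduce the dose to 90 mg or pause dosing at any time. The first 210 mg dose may be given only after the DMC has reviewed at least 3 subjects who completed Week 6 at 150 mg, including adverse events and injection-site reactions, Week 6 laboratory tests and ECG, and MRI where read, and has recommended the increase.

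Keep the existing DMC review after 3 subjects complete Week 6 at the new dose. In Section 8.3, also refer to the Week 6 review, since its parenthesis mentions only reviews when subjects complete treatment.

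The change reuses the protocol's own DMC trigger, adds no visit or test, and leaves reductions immediate. Its cost is time: the first 210 mg dose comes no sooner than about 6 weeks after the third subject's first dose, plus DMC time. At an assumed 4 or 5 subjects per month and 2 weeks for the DMC, only 2 or 0 of 12 places would remain for 210 mg, so a short enrollment pause would be needed to evaluate that dose. That is acceptable, since the objective in Section 3 is stated for 150 mg.

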## **8.4. Study Drug Accountability**

Site personnel must maintain an accurate drug accountability record of the receipt and dispensing of study drug. The Site Monitor will verify study drug accountability during monitoring visits.

Site personnel must administer study drug only to individuals enrolled in the study. Administration of study drug must be recorded in the subject's source documents, the eCRF, and the study drug inventory log.

## **8.5. Study Drug Handling and Disposal**

Only after receiving written authorization by AmMax or its designee, the Investigator will send all unused and empty vials of study drug to the address provided at the time of authorization for destruction.

With specific approval from AmMax, unused and empty vials of study drug may be destroyed at the site, following the standard operating procedures at the study site. The study staff must provide a drug destruction certificate to AmMax or its designee.

